1.3 Findings from Non-Clinical and Clinical Studies

1.3.1 Clinical studies

When anterior spinal fusion is selected it is more often performed in cases where only one curve, the thoracic or the lumbar curve, requires a fusion [23]. We are proposing similar indications and applications for vertebral tethering – a single thoracic curve requiring treatment. Anterior spinal fusion provides good clinical and radiographic results. The approach for anterior spinal fusion for AIS is most often performed with thoracoscopic guidance. The thoracoscopic approach is less invasive than its alternative, an open thoracotomy. Newton et al. reported on 5 year results of thoracoscopic anterior fusion showing that Cobb angle correction averaged 56% [20, 24], and total lung capacity at 91% of expected. These results were not different than the 2 year outcomes in the same patients, suggesting that any slight negative impact of anterior thoracoscopy did not lead to a progressive decline in pulmonary function. Furthermore, although open anterior spinal fusion is associated with a significant decline in objective measurements in pulmonary function, thoracoscopic anterior surgery was not different in its impact on pulmonary function than posterior spinal fusion [25, 26]. Faro et al. demonstrated that pulmonary function declines 3 months after both open and thoracoscopic anterior scoliosis surgery but recovers by 1 year post-op in thoracoscopic surgery but not in open anterior surgery [27].

In a comparison of the three approaches for fusion of the thoracic spine for AIS (open anterior, thoracoscopic anterior, and posterior), Newton et al. in another study reported that Cobb angle correction (57%) was similar in all groups, blood loss and incidence of transfusion was greater but surgical time was less in the posterior group, and SRS-22 scores were equivalent [18]. Furthermore, they reported decreased pulmonary function in the open anterior groups but similar PFTs in posterior and thoracoscopic patients. Lonner et al. also addressed the impact of surgical approach on pulmonary function [23]. The authors reported a decrease in forced expiratory volume in 1 second (FEV1) and functional vital capacity (FVC) as a percent of expected by 4-5% but an increase in total lung capacity (TLC) of 3% (Tables 1 and 2). These changes are of minimal clinical significance.

Table 1: Demographics (Adapted from Lonner et al, 2015)

Other authors have also reported on high long term re-operation rates following AIS fusion surgery ranging from 4.6% to 19% [29-31]. One theory is that a fusion imparts increased stress on unfused segments below a fusion. Marks et al. have shown that patients will retain total lumbar motion after a posterior spinal fusion by increasing motion in the unfused areas [32]. The authors postulate that increased motion may lead to degeneration of discs and facet joints. These findings of supraphysiologic motion below a posterior spinal fusion may explain some of the decreasing durability of posterior spine fusion. Green et al. have studied the health of intervertebral discs below a spinal fusion at an average of 11.8 years following posterior spinal fusion [33]. The authors found that disc degeneration was occurring in 85% of patients and the discs when graded by the Firman scale, an objective validated measure of disc degeneration [33]. Vertebral tether surgery will allow for continued motion of the instrumented levels and thus avoid the long leverarm effect of a long fusion that may be contributing to early degeneration. Additional reports have questioned the durability of posterior spinal fusion. Upasani et al. reported on increased pain in patients at 5 years post-spinal fusion compared to at 2 years [34]. Lastly, posterior spinal fusion in patients who have not had their pubertal growth spurt, the population in whom we are proposing vertebral tethering, are at increased risk of complications and re-operation. Sponseller et al. reported that patients with open triradiate cartilages undergoing spinal fusion surgery have an increased rate of "adding on" (development of deformity below a fusion) and the response of the uninstrumented lumbar curve is less predictable [35].

Ideally, longitudinal outcomes of current standards of care including anterior thoracoscopic and posterior pedicle screw instrumented fusion would be used as a standard against which new technology can be compared. However, such data is a half century away. Furthermore, the pace of change and improvement in spinal deformity instrumentation and surgery tells us that change is inevitable [36].

1.3.2 Non clinical studies

There have been several animal studies of vertebral tethering. Peter Newton and colleagues at The University of California at San Diego and Rady Children's Hospital have performed spinal tethering studies in bovine and porcine models [37-39]. The first study the authors published was in an immature bovine model [38]. They utilized a stainless steel tether. They demonstrated those animals who had a sham surgery without placement of the tether did not develop a curvature while those with placement of two rods did develop a curve. This was offered as a proof of concept that tension of a tether could alter growth and change alignment. In the porcine model, the investigators demonstrated the ability of a spinal tether to induce deformity in immature animals proportionally to the duration it was left in place, offering further evidence of the effect of growth in contributing to the deformity rather than tension of the implant alone [40]. Further evidence of the effect of growth driving the change in alignment was offered in a subsequent study of the bovine model [37]. They demonstrated equivalent deformity magnitude after 12 months between groups in which the tether was tensioned and those in which it was placed without tension.

1.4 Relevant Literature and Data

The natural history of scoliosis after maturity has been described in several populations treated non-operatively and followed longitudinally. One cohort is from Scandinavia and was reported by Danielsson and Nachemson [41]. The other is from Iowa and was reported by Weinstein and colleagues [42, 43]. Nachemson reported a cohort of 117 scoliosis patients with a variety of types of scoliosis including those classified as congenital scoliosis, neuromuscular scoliosis, postinfectious scoliosis, and idiopathic scoliosis [44]. Decreased life expectancy was reported in this group. A subsequent sub-analysis of only the idiopathic scoliosis patients in this group revealed that there was no increase in mortality compared to the general population. Weinstein et al. reported a group of idiopathic scoliosis patients treated with observation [43]. They showed that, despite an increase in back pain symptoms, there was no increase in mortality rates compared to the aged matched general population. Furthermore, they identified Cobb angle greater than 50 degrees as a predictor of continued progression in adulthood. Greater than 85% of these patients progressed at a rate of ~1.1 degrees per year. Weinstein demonstrated a Cobb angle greater than 50 degrees as a factor predictive of further progression in adolescents in a subsequent study [42]. This forms the basis for current indications of surgical fusion for curves greater than 50 degrees. Conversely, curves less than 30 degrees at the end of growth did not progress nor did they exhibit any pain or pulmonary dysfunction. The desire to keep curves below thirty degrees forms the recommendation for initiation of brace management in curves that are 25-30 degrees.

1.4.1 Curves below 50 Degrees With A High Likelihood of Progression to 50 Degrees

Further studies have elucidated which curves in immature patients will progress to 50 degrees before reaching skeletal maturity. Rather than taking a reactive approach to these curves, we propose early treatment of this population with vertebral tethering. Dimeglio et al. demonstrated that immature patients with idiopathic scoliosis with a Cobb angle of 30 degrees or greater prior to their pubertal growth spurt will universally progress to 50 degrees by the end of growth [45].

Dimeglio suggests several measures for identifying the onset of 10 pubertal growth spurt including the changes of various bone growth centers remote from the spine. These include the appearance (radiographically) of the sesamoid bone in the thumb, the presence of two distinct ossification centers in the olecranon (elbow), and an open tri-radiate cartilage (hip socket). Sanders et al. have also demonstrated a correlation of risk of progression to a Cobb angle of 50 degrees between markers of skeletal maturity and Cobb angle [46]. They developed an easily applied scoring system of 1-7 to a hand x-ray. The advantage of a hand x-ray is that it encompasses a large number of growth centers, does not require additional training of radiology personnel, and is remote from more radiosensitive organs. The maturity based progression assessment derived by Sanders assigns a risk of progression to a Cobb angle of 50 degrees or more. It is this risk of progression to 50 degrees on which we base or treatment decision for Vertebral Body Tethering. **Table 3** illustrates that there is significant risk for progression if a patient's curve is above 35 degrees, and is a Sanders stage of 4 or less. Therefore our inclusion criteria for this study are set to include patients with curves above 35 degrees and a Sanders stage of 4 or less.

We have selected an upper limit of 60 degrees due to the theoretical concern of achieving higher amounts of correction during periods of limited growth. In retrospective series by Samdani et al., the average Cobb angle of treated curves was 44 degrees [21, 22].

Table 3: Projected risk of progression of scoliosis to above 50 degrees, based on curve magnitude and bone age. (From Sanders, et al. 2008)

TABLE	III Logistic Projectio	n of the Probability o	f Lenke Type-1 and T	ype-3 Curves Progi	ressing to Surgery	Assuming a >50	° Threshold*†
Curve	Stage 1	Stage 2	Stage 3	Stage 4	Stage 5	Stage 6	Stage 7, 8
10°	2%	0%	0%	0%	0%	0%	0%
	(0% to 40%)	(0% to 15%)	(0% to 0%)	(0% to 0%)	(0% to 0%)	(0% to 0%)	(0% to 1%)
15°	23%	11%	0%	0%	0%	0%	0%
	(4% to 69%)	(1% to 58%)	(0% to 2%)	(0% to 0%)	(0% to 0%)	(0% to 0%)	(0% to 7%)
20°	84%	92%	0%	0%	0%	0%	0%
	(40% to 98%)	(56% to 99%)	(0% to 14%)	(0% to 1%)	(0% to 1%)	(0% to 1%)	(0% to 26%)
25°	99%	100%	29%	0%	0%	0%	0%
	(68% to 100%)	(92% to 100%)	(3% to 84%)	(0% to 5%)	(0% to 5%)	(0% to 2%)	(0% to 64%)
30°	100%	100%	100%	0%	0%	0%	0%
	(83% to 100%)	(98% to 100%)	(47% to 100%)	(0% to 27%)	(0% to 22%)	(0% to 11%)	(0% to 91%)
35°	100%	100%	100%	0%	0%	0%	0%
	(91% to 100%)	(100% to 100%)	(89% to 100%)	(0% to 79%)	(0% to 65%)	(0% to 41%)	(0% to 98%)
40°	100%	100%	100%	15%	0%	0%	0%
	(95% to 100%)	(100% to 100%)	(98% to 100%)	(0% to 99%)	(0% to 94%)	(0% to 83%)	(0% to 100%)
45°	100%	100%	100%	88%	1%	0%	0%
	(98% to 100%)	(100% to 100%)	(100% to 100%)	(2% to 100%)	(0% to 99%)	(0% to 98%)	(0% to 100%)

^{*}Unshaded cells correspond with combinations of curve size and maturity stage for which surgery would be a plausible treatment if >50° at maturity is accepted as the threshold for surgical treatment. Shaded cells correspond with combinations for which surgery would not be a plausible treatment. †Cells with wide 95% confidence intervals (shown in parentheses) correspond with groups that had too few patients for accurate estimates (or groups that had no patients) and should be interpreted with caution.

1.5 Compliance Statement

This study will be conducted in full accordance with all applicable Nemours Research Policies and Procedures and all applicable Federal and state laws and regulations including 45 CFR 46, 21 CFR Parts 50, 54, 56, 312, 314 and 812 and the Good Clinical Practice: Consolidated Guideline

approved by the International Conference on Harmonization (ICH). All episodes of noncompliance will be documented.

The investigators will perform the study in accordance with this protocol, will obtain consent and assent, and will report unanticipated problems involving risks to subjects or others in accordance with Nemours IRB Policies and Procedures and all federal requirements. Collection, recording, and reporting of data will be accurate and will ensure the privacy, health, and welfare of research subjects during and after the study.

2 STUDY OBJECTIVES

The purpose of the study is to determine the safety and efficacy of Anterior Vertebral Body Tethering surgery on patients with Idiopathic Scoliosis.

2.1 Primary Objective (or Aim)

The primary objective is to assess the safety of Anterior Vertebral Body Tethering surgery in the immediate post-operative period.

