The study intervention is surgical orthopedic implantation of Anterior Vertebral Body Screws with PET cord, by way of thoracoscopic surgery under general anesthesia. The primary outcome measures include assessments of safety of the insertion procedure and of the device, as well as the secondary measure of efficacy by determining the improvement in the angle of deformity. Monitoring will be conducted by a data safety committee, who has extensive training and experience in surgical procedures.

PROTOCOL SYNOPSIS

Study Title

Safety and efficacy of a vertebral body tethering technique for

pediatric idiopathic scoliosis

Funder

Departmental Funds

Clinical Phase

Phase II

Study Rationale

Anterior surgical approach and instrumentation is an accepted standard treatment for idiopathic scoliosis (IS). This study will assess whether the intervention (Anterior Vertebral Tethering) is a safe and efficacious method of anterior approach surgery for spinal deformity in pediatric scoliosis.

Study Objective(s)

Primary

To determine the safety of Anterior Vertebral Tethering surgery

Secondary

To determine the efficacy of Anterior Vertebral Tethering

Test Article(s)

Globus Medical Inc.

Reflect/TransitionTM Stabilization System Polyethylene terephthalate (PET) cord

Study Design

This is a single center prospective, open-label pediatric clinical device trial with a single surgical intervention with retrospective arm to collect data from patients who already had AVT surgery.

Subject Population Key criteria for Inclusion and Exclusion:

Inclusion Criteria

- 1. Males or females age 8 to 16 years old at time of enrollment (inclusive)
- 2. Diagnosis of Idiopathic Scoliosis
- 3. Sanders bone age of less than or equal to 4
- 4. Thoracic curve of greater than or equal to 35 degrees but not larger than 60 degrees
- 5. Lumbar curve less than 35 degrees
- 6. Spina bifida occulta is permitted
- 7. Spondylolysis or Spondylolisthesis is permitted, as long as it is non-operative, the patient has not had any previous surgery for this, and no surgery is planned in the future
- 8. Completed standard-of-care procedures as outlined in Section 5

Subject Population Key criteria for Inclusion and Exclusion:

Exclusion Criteria

- 1. Pregnancy (current)
- 2. Prior spinal or chest surgery
- 3. MRI abnormalities (including syrinx >4mm, Chiari malformation, or tethered cord)
- 4. Neuromuscular, thoracogenic, cardiogenic scoliosis, or any other non-idiopathic scoliosis

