3.1.3 Post-operative follow-up

The Post-operative follow-up phase of the study will last approximately 90 days, beginning with the day after the surgical intervention. This period has 2 set time points for follow-up, which will occur during standard-of-care clinical follow-up visits for spine patients receiving surgical intervention. The two time-points are a POD-45 clinical visit, and a POD-90 clinical visit. During these two clinical visits physical exams, radiographs, and AE / SAE data will be collected. POD 2-44 will be monitored for known complications and AE / SAEs only, as there will be no clinical outcomes data to collect during this time. This data will be abstracted from the medical records. In addition, the patient will be under SOC post-operative care for patients who have undergone Anterior Spinal Surgery. Data from any SOC interventions will also be abstracted from the medical record.

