6 STATISTICAL CONSIDERATIONS

6.1 Primary Endpoint

The primary endpoint is the rate of Adverse Events/SAEs in Anterior VBT Surgery.

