6.3.2 Safety Analysis

The safety endpoint will be factors associated with the adverse events in patients that have undergone Anterior VBT Surgery. Variable reporting for adverse event will be dichotomous. Descriptive statistics will be used to report number and type of adverse events. Further, chi-square or fisher-exact test analysis will be used to identify variables that correlate with adverse events following anterior tethering surgery. Further, logistic regression will be conducted to clarify which variables are associated with adverse outcomes. Odds ratio along with confidence intervals will be reported.

All subjects will begin the safety analysis at Study Day 0 (day of surgery). Intraoperative and post-intervention medical events or signs and symptoms of the complications arising after the start of study intervention will be captured using list of common events associated with Anterior VBT Surgery. Adverse signs, symptoms, and/or laboratory abnormalities already existing prior to the baseline visit will be captured in the medical history assessment.

The date of onset, severity, and end date (if relevant) will be documented.

Medical events resulting from any procedure performed in the study will be collected as adverse events (AEs). The event description, date of onset, end date, severity, and outcome will be documented for the study-related AEs. The frequencies of AEs by type, body system, severity and relationship to study intervention will be summarized. SAEs (if any) will be described in detail. A distinction will be made between those AE/SAEs which are "device-related", those which are "not device-related", and those which are "uncertain to be related". "Device-related" complications will include any events directly related to the integrity, safety, or biomechanics of the PET cord. Device-related AE incidence will be summarized along with the corresponding exact binomial 95% two-sided confidence intervals. 22

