6.6.2 Stopping rules for SAEs that are device-related
Definition of Terms:
□ Screw failure – screw and/or centering staple have loosened from the vertebra AND require re- operation
☐ Tether failure – the tether has broken or lost tension. Diagnosed at any time point after 3 months by increased angulation at a disc space on standing PA or increase in disc wedging on side bending x-ray to the side away from the implant. Also, it is only an SAE if noted before maturity AND overall Cobb worsens compared to the first erect measurement
☐ Implant re-operation - any problem with the implant that requires re-operation including re-operation for overcorrection with any of the following: a removal of all or part of the implant, loosening of the tension on the implant, or spinal fusion.

Stopping Points
☐ Screw failure stopping point: 3 of first 5 cases, 5 of first 10, or 25% of patients beyond 20
cases
☐ Tether failure stopping point: 3 of first 5 cases, 5 of first 10, or 25% of patients beyond 20
cases
☐ Implant failure re-operation stopping point: occurs in 4 of first 5 cases or greater than 50% of
cases beyond 10 cases

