8.4 Recording plan for AE / SAEs

Surgery and Post-operative Phase (Day 0 – POD 90):

For these phases, all AEs (including SAEs) will be noted in the study records and reported per IRB and FDA requirements outlined below. The subjects will be encouraged to contact the office with any concerns, and the medical record will be monitored by study staff for indications of AEs.

Extended Follow-up Phase (POD 91-POD 1825):

For this phase, all SAEs will be recorded (regardless of cause). Only AEs which are deemed "device related" will be recorded on study documents and reported per IRB and FDA requirements outlined below. The subjects will still be encouraged to contact the office with any concerns, and the medical record will be monitored by study staff for indications of SAEs or device-related AEs.

Only the AE/SAEs indicated above will be recorded in a patient-specific study binder, kept in the secure Orthopedics research office. The binder will contain a full description of the event, including the nature, date and time of onset, determination of non-serious versus serious, intensity (mild, moderate, severe), duration, causality, and outcome of the event. Hard copies of the primary documents (medical record notes) describing the event and any associated treatment will be printed and kept in the patient-specific study binder. A redundant copy of adverse events will be kept in the study REDCap database and will be maintained by the study team separately from the patient-specific study binder. The study binder will serve as the official record of all Events.

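### The primary safety endpoint is inconsistently defined: the synopsis and Sections 2.1, 6.1 and 6.3.2 differ on window and content, none gives a counting unit, and AE recording narrows after POD 90

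*Combined protocol and SAP*

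**What the plan says.** All references are to the combined protocol and SAP.

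- **Objective.** Section 2.1 ties the primary objective to the "safety of Anterior Vertebral Body Tethering surgery in the immediate post-operative period" and does not define that period. The synopsis puts it as "To determine the safety of Anterior Vertebral Tethering surgery", with no time limit. Section 5.2 also calls safety a primary objective without limiting the period.
- **Endpoint.** Section 6.1: "The primary endpoint is the rate of Adverse Events/SAEs in Anterior VBT Surgery". It gives no start, no end, and no indication of whether patients or events are counted.
- **Analysis.** Section 6.3.2: "The safety endpoint will be factors associated with the adverse events in patients that have undergone Anterior VBT Surgery". The same section starts the safety analysis on the day of surgery and names no end. It plans descriptive counts of AEs by number and type, and exact binomial 95% intervals for device-related AE incidence only.
- **Phase-specific endpoints.** The Safety Evaluations part of the synopsis lists separate measures for surgery, the post-operative phase and extended follow-up. The last includes over-correction, implant failure on serial x-ray, curve progression and re-operation. Section 6.1 does not refer to this list.
- **Recording.** Section 8.4 (Recording plan) captures all AEs and SAEs from Day 0 to POD 90. From POD 91 to POD 1825 it captures every SAE, but non-serious AEs only when device-related.
- **Tether failure.** Section 6.6.2 defines it, for the stopping rules, as "Diagnosed at any time point after 3 months", on radiographic criteria.

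**The concern.** A primary endpoint should identify one number. Here the objective, the endpoint and the analysis section describe different things, and the recording rule changes partway through follow-up. Two natural ways of computing the Section 6.1 rate each have a fault. A short window, as 2.1 suggests, leaves out the late loss or breakage of the tether that 6.6.2 singles out. A single rate over all follow-up counts ordinary AEs for the first 90 days and then stops counting them, so it is neither an early rate nor a five-year rate for that class of event.

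Since no section chooses between these, the choice could be made after the data are seen. The study is open-label, has one cohort, and is run by a sponsor-investigator. The same patients could then support quite different headline statements about safety.

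**Working it through.** The plan states no expected AE rate, precision or power (Section 6.4), so there is no figure to reproduce. The check sets the definitions against each other and then illustrates the size of the effect.

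**Step 1. Which events can enter the rate under each window.** Section 3.1.3 says "The Post-operative follow-up phase of the study will last approximately 90 days". I take POD 90 as the longest plausible reading of the period in 2.1; this is an assumption, because 2.1 gives no number.

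| Event class | Day 0 to POD 90 | POD 91 to POD 1825 |
|---|---|---|
| SAE, any cause | recorded | recorded |
| Device-related AE | recorded | recorded |
| Non-serious, non-device-related AE | recorded | not recorded |
| Tether failure as defined in 6.6.2 | cannot be diagnosed | can be diagnosed |
| Screw failure, implant re-operation (6.6.2) | can count | can count |
| Cord breakage, as a device-related event (5.2, 8.4.1) | can count | can count |

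Only the third row changes capture rule, and only the fourth is removed by a 90-day window. Section 3.3.1 allows three weeks' grace, so the POD-90 visit may fall as late as 90 + 21 = POD 111. Events therefore have to be assigned by onset date, not by visit.

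**Step 2. Effect of the window.** N = 30 (Section 3.3.2, both arms). Assumed events: 7 subjects with late tether failure and no other events. For scale, 7/30 = 23.3% is just under the 25% tether-failure stopping point in 6.6.2. Exact (Clopper-Pearson) intervals:

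- To POD 90: 0/30 = 0%. Upper limit 1 − 0.025^(1/30) = 11.6%. Interval 0 to 11.6%.
- To POD 1825: 7/30 = 23.3%. Lower limit is the 2.5% point of Beta(7, 24) = 9.9%; upper limit is the 97.5% point of Beta(8, 23) = 42.3%.

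**Step 3. Effect of mixed capture.** All rates here are assumed, and the events are taken as independent. Let e = 30% of subjects with an AE by POD 90, t = 10% or 25% with later tether failure, and u = 5% to 30% with a later non-serious, non-device-related AE that is not recorded.

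- Recorded five-year rate, 1 − (1 − e)(1 − t): 1 − 0.70 × 0.90 = 37%; 1 − 0.70 × 0.75 = 47.5%.
- Rate with full recording, 1 − (1 − e)(1 − t)(1 − u): 40% to 56% when t = 10%; 50% to 63% when t = 25%.

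The gap between recorded and full rates depends entirely on u, for which the documents give no value.

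**The case against.** The strongest reply is that the plan already contains most of what is needed. The synopsis reports safety by phase, which neither hides late failures nor pools capture rules. SAEs and device-related AEs are recorded under one rule to POD 1825. Section 6.3.2 already summarises device-related AE incidence with exact intervals. Late failures also feed the stopping rules. Making peri-operative safety primary, with later device outcomes reported separately, is a legitimate choice for a single-arm study with no hypothesis test.

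Most of this stands, and it rules out several stronger readings that a reader might infer:

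- *The rate must either exclude tether failures or mix capture rules.* Not so: reporting by phase is a third reading. The difficulty is that 6.1 does not adopt it and 2.1 points elsewhere.
- *A 90-day window excludes device failures.* Only tether failure as worded for the stopping rules is excluded. Early cord breakage, screw failure and implant re-operation can still count.
- *The long period after POD 90 measures the bias.* A share of calendar days says nothing about how many events go unrecorded, and those events are confined to one class.
- *Section 6.3.2 replaces the rate with an association analysis.* Its sentence on the endpoint is badly worded, but descriptive counts are still planned.
- *Late failures escape monitoring.* They do not. The gap is in the primary endpoint.

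What the reply leaves unanswered is which of these outputs is the primary result.

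**Conclusion.** The concern holds as an inconsistency in the definition of the primary safety endpoint. The window is undefined in 2.1 and absent from 6.1, the counting unit is missing, 6.3.2 describes a different quantity, and the phase-specific endpoints in the synopsis are not tied to 6.1. Applied literally, 6.1 pools two capture rules for non-serious, non-device-related AEs, while 2.1 read as about 90 days keeps tether failure as defined in 6.6.2 out of the primary result.

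The practical size cannot be fixed from the documents. The illustration shows that the choice of window alone can move the headline from 0% to 23.3% in the same 30 subjects. That rests on an assumed event count, on POD 90 as the end of the early period, and on complete follow-up. It should be corrected before analysis. It does not undermine the recording of device events or the stopping rules.

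**What to change.** Reconcile 2.1, 6.1 and 6.3.2 with the synopsis by stating two safety endpoints that follow the existing recording boundary:

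1. **Early:** the proportion of implanted subjects with at least one AE or SAE with onset from Day 0 to POD 90, with an exact 95% interval.
2. **Long-term:** the cumulative incidence of any SAE or device-related AE through POD 1825, by a time-to-first-event estimate that allows for withdrawal and incomplete follow-up.

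Base the safety conclusion on both. Label the chi-square, Fisher and logistic analyses of factors related to AEs as exploratory. Use one definition of device-related for the second endpoint: 5.2 lists cord, staples, set screws and vertebral screws, whereas 6.3.2 names only the cord. The 30 subjects in 3.3.2 include a retrospective arm whose early AE capture is not described, so report that arm separately for the first endpoint unless its capture is shown to be equivalent.

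The cost is protocol and SAP wording. For prospective subjects the recording already planned is sufficient; for the retrospective arm this has to be checked. The headline safety figure may be less favourable, because late device events would count.
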